10.1.4.2 Evaluation of Non-Target Lesions

Complete Response (CR): Disappearance of all non-target lesions and

normalization of tumor marker level. All lymph nodes must be non-pathological in size (< 10 mm short axis).

Note: If tumor markers are initially above the upper normal limit, they must normalize for a subject to be considered in complete clinical response.

Incomplete Response/Stable Disease (SD): Persistence of one or more non-target lesions and/or maintenance of tumor marker level above the normal limits.

Progressive Disease (PD): Appearance of one or more new lesions* (new lesions must be > slice thickness) and/or unequivocal progression of existing non-target lesions. Overall level of substantial worsening that merits discontinuation of therapy. A useful test that can be applied when assessing non-targets for unequivocal progression is to consider if the increase in overall disease burden based on the change in non-measurable disease is comparable in magnitude to the increase that would be required to declare PD for measurable disease.

Unknown (UN): Assessment of non-target lesions cannot be made due to insufficient or unevaluable data. In this case, a concise explanation must be given.

***Definition of New Lesion:** The finding of a new lesion should be unequivocal (i.e. not due to difference in scanning technique, imaging modality, or findings thought to represent something other than tumor (ex: new bone lesions may be healing or flare of pre-existing lesions). However, a lesion identified on a follow-up scan in an anatomical location that was not scanned at baseline is considered new and will indicate PD. If a new lesion is equivocal (because of small size, etc.), follow-up evaluation will clarify if it truly represents new disease and if PD is confirmed, progression should be declared using the date of the initial scan on which the lesion was discovered.

10.1.4.3 Evaluation of Best Overall Response

The best overall response is the best response recorded from the start of the treatment until disease progression/recurrence (taking as reference for progressive disease the smallest measurements recorded since the treatment started). The participant's best response assignment will depend on the achievement of both measurement and confirmation criteria.

For Patients with Measurable Disease (i.e., Target Disease)

Target Lesions	Non-Target Lesions	New Lesions	Overall Response	Best Overall Response for when Confirmation is Required:
CR	CR	No	CR	≥ 4 wks confirmation
CR	Non-CR/Non-PD	No	PR	≥ 4 wks confirmation
CR	Not evaluated	No	PR	
PR	Non-CR/Non-PD/Not evaluated	No	PR	
SD	Non-CR/Non-PD/Not evaluated	No	SD	Documented at least once ≥ 4 wks from baseline
PD	Any	Yes, or No	PD	No prior SD, PR or CR
Any	PD*	Yes, or No	PD	
Any	Any	Yes	PD	
* In exceptional circumstances, unequivocal progression in non-target lesions may be accepted as disease progression.				
Note: Participants with a global deterioration of health status requiring discontinuation of treatment without objective evidence of disease progression at that time should be reported as " symptomatic deterioration ". Every effort should be made to document the objective progression even after discontinuation of treatment.				

For Patients with Non-Measurable Disease (i.e., Non-Target Disease)

Non-Target Lesions	New Lesions	Overall Response
CR	No	CR
Non-CR/non-PD	No	NonCR/non-PD
Not all evaluated	No	Not evaluated
Unequivocal PD	Yes, or No	PD
Any	Yes	PD
Non-CR/non-PD is preferred over stable disease for non-target disease since SD is increasingly used an endpoint for assessment of efficacy in some trials so to assign this category when no lesions can be measured is not advised.		

10.1.5 Duration of Response

Duration of overall response: The duration of overall response is measured from the time measurement criteria are met for CR or PR (whichever is first recorded) until the first date that recurrence or PD is objectively documented, taking as reference for PD the smallest measurements recorded since the treatment started.

Duration of overall complete response: The duration of overall CR is measured from the time measurement criteria are first met for CR until the first date that recurrent disease is objectively documented.

Duration of stable disease: Stable disease is measured from the start of the treatment until the criteria for progression are met, taking as reference the smallest measurements recorded since the treatment started.

10.1.6 Progression-Free Survival

Progression-Free Survival (PFS) is defined as the duration of time from study registration to the date of documented disease progression or death, whichever occurs first. Patients not experiencing an event will be censored at the date of the last disease assessment.

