5.3 Pretreatment Criteria

The first dose of Everolimus may be administered on the same day as enrollment but no more than 10 business days after enrollment. The treatment period begins on the first day of treatment with Everolimus.

If a subject is unable to come into the clinic for a required study visit or if unforeseen events occur, the visit procedures may be performed within a one week time frame.

The following assessments will be performed at each clinic visit according to table 3.4 throughout the treatment period:

- Physical examination,
- ECOG performance status,
- Blood pressure, respiratory rate, resting pulse, temperature, and weight.
- Laboratory evaluations: If patients have met trial eligibility within the previous 72 hours, no specific criteria will need required in order to initiate the protocol unless, in the investigator's opinion, significant medical issues arise which would contraindicate starting the study medications. If patients have completed entry criteria >72 hours prior to cycle 1 day 1, laboratory values on cycle 1 day 1 should be repeated to confirm all eligibility criteria are met.
- CT scans (contrast-enhanced) or MRI scan (contrast-enhanced) or PET-CT scan of areas of known disease every 8 weeks with a 5 business-day time window in case unforeseen events occur. Evaluation according to RECIST criteria compared to previous scan.
- beta HCG pregnancy test for women of child-bearing potential

Documentation of all adverse events will occur at each clinic visit and at any other time point when necessary. There are no specific criteria for the initiation of a given cycle except for the ones indicated in the dose modification tables 6-2, 6-3 & 6-4. Study subjects may commence with treatment if, in the opinion of the investigator and based on the guidance of Section 6, it is safe for the participant to do so.

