5.7 Duration of Follow Up

Participants will be followed until death after removal from treatment. This follow-up will be performed by review of the medical record, contact with care providers, and/or telephone contact as needed every 3 months.

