14.1 Study Design/Endpoints

The primary objective of this trial is objective response rate according to RECIST 1.1 criteria.

Secondary objectives include duration of response, progression-free and overall survival. Duration of response is defined as the time from RECIST-confirmed response (CR+PR) to documented disease progression. Progression-free survival is defined as the time from study registration to documented disease progression per RECIST 1.1 or death from any cause, whichever occurs first. Patients not experiencing a PFS event will be censored at the date of their last disease assessment. Overall survival is defined as time from registration to death from any cause, censoring patients thought to be alive at the time of final analysis at the last date of follow up. We will also estimate toxicity via CTCAE version 4.0, and the association of IHC and whole exome sequencing results with patient outcomes and other genetic events.

We will estimate event-time distributions using the Kaplan-Meier method, using Greenwood's formula to estimate the variance and provide 90% confidence intervals for the medians, 6-month, and 1-year estimates. Categorical outcomes, such as toxicity and response, will be estimated and their corresponding 90% exact binomial confidence intervals will be provided.

For the cohort of patients with TSC1 and TSC2 mutations, we will conduct this study using a Simon's two-stage design. In the first stage we will enroll 21 patients and if a total of at least 4 responses (CR + PR) are observed among them, accrual to the second stage will open. If 3 or fewer responses are observed among the first 21 patients, the study will terminate. In the second stage, an additional 29 patients will be enrolled for a total study accrual of 50 patients. After accrual to the second stage is completed, we will declare study success if at least 8 responses are observed among the 50 registered patients. This design has a probability of stopping early after the first stage of accrual of 85% if the drug is ineffective; the overall power of the study to detect the targeted response rate of 30% (compared to a null of 10%) is 91% while controlling the type I error at a one-sided level of 0.07.

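### No tumour assessments are scheduled once everolimus stops without progression, yet any later death counts as a PFS event, so PFS is usually overstated when follow-up is mature

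*Combined protocol and SAP*

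**What the plan says.** **Event and censoring rule.** Section 10.1.6 defines PFS as "the duration of time from study registration to the date of documented disease progression or death, whichever occurs first". Section 14.1 agrees: "Progression-free survival is defined as the time from study registration to documented disease progression per RECIST 1.1 or death from any cause, whichever occurs first". Censoring applies only to patients without an event. Section 10.1.6 puts it as "Patients not experiencing an event will be censored at the date of the last disease assessment", and 14.1 as "Patients not experiencing a PFS event will be censored at the date of their last disease assessment". Neither section limits how long after the last scan a death may fall and still count at its own date. Neither says what happens after missed assessments or new anticancer therapy.

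**Scans during treatment.** Section 5.3 introduces its list with "The following assessments will be performed at each clinic visit according to table 3.4 throughout the treatment period", and the list includes scans "of areas of known disease every 8 weeks with a 5 business-day time window in case unforeseen events occur". The Section 9 calendar has an 8-weekly scan column capped at 24 months. Its End of Study column shows no scan, and it has no column for imaging after treatment.

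**After treatment.** Section 5.6 foresees stopping for intercurrent illness, adverse events, non-compliance, patient choice or investigator judgement, as well as for progression. Section 5.7 then follows participants to death: "This follow-up will be performed by review of the medical record, contact with care providers, and/or telephone contact as needed every 3 months". It names no imaging.

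**Text pointing the other way.** The opening of Section 10 asks for response re-evaluation every 8 weeks, and for a confirmatory scan 4–8 weeks after a first response, without limiting either to time on drug. The note on symptomatic deterioration in 10.1.4.3 adds: "Every effort should be made to document the objective progression even after discontinuation of treatment".

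**The concern.** Progression can enter the data only if someone looks for it. During treatment that happens every 8 weeks. After a stop without progression no schedule is clearly set, but deaths continue to be collected. An unseen progression followed by death is then recorded as progression-free time up to the death. The same unseen progression in a patient still alive is recorded as censoring at the last scan, which may itself be informative.

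Section 14.1 plans Kaplan-Meier medians and 6-month and 1-year estimates with 90% confidence intervals. In a single-arm trial readers will set these figures beside outside data, and no control arm shares the distortion.

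**Working it through.** The plan states no PFS assumption, event count or PFS power, so there is no figure to reproduce. The check has two parts.

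**1. The rules applied to two hypothetical patients.** Eight weeks is 56/30.4 = 1.84 months. Both patients stop for toxicity at month 2, having been scanned at month 1.84. Both progress, unscanned, at month 4.
- Under continued 8-weekly scanning, progression is seen at the third scan: 3 × 1.84 = 5.5 months.
- As written, the patient who dies at month 14 has PFS = 14 months, equal to overall survival. The excess is 14 − 5.5 = 8.5 months.
- As written, the patient alive at the cut-off is censored at about month 1.8.

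**2. Size, by simulation.** There were 200,000 patients per scenario, with exponential times. From the documents: 8-week scans and 48-month accrual (14.3). Assumed, because the documents give nothing: median time to progression 3–6 months, median survival after progression 4–12 months, share stopping without progression set at 10–30%, 12 months of follow-up after last entry, and no off-treatment progression ever documented. Three rules were compared: (a) scans continue after stopping; (b) the plan as written; (c) as (b), but a death more than two scan intervals after the last scan is censored at that scan.

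Selected results for (a) → (b). The share that actually stopped in the run is in brackets. The last two rows lie outside the main grid.

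| Median progression / post-progression survival (months) | Stop setting | 6-month PFS | 12-month PFS |
|---|---|---|---|
| 4 / 8 | 10% (11%) | 34.5 → 36.7 (+2.2) | 11.9 → 14.7 (+2.8) |
| 4 / 8 | 20% | 34.6 → 39.7 (+5.1) | 11.9 → 18.2 (+6.3) |
| 4 / 8 | 30% (35%) | 34.5 → 43.0 (+8.5) | 11.9 → 22.0 (+10.1) |
| 6 / 12 | 10% (11%) | 49.4 → 50.5 (+1.1) | 24.1 → 26.0 (+1.9) |
| 6 / 12 | 30% (32%) | 49.0 → 53.1 (+4.1) | 24.1 → 30.6 (+6.5) |
| 12 / 24 | 30% (29%) | 70.2 → 70.7 (+0.5) | 49.3 → 50.5 (+1.2) |
| 18 / 12 | 30% (26%) | 78.9 → 79.2 (+0.3) | 62.2 → 62.6 (+0.4) |

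- Over the main grid, (b) exceeds (a) by about 1–12 points at 6 months, 1–13 points at 12 months, and 0–1.9 months in the median. Medians fall on scan dates, so a shift of 1.8–1.9 months is one scan interval. If progression speeds up after stopping, the 6-month excess reached 16 points.
- In the main grid 65–92% of stoppers had died by the cut-off. Of those deaths, 80–92% came more than two scan intervals after the last scan.
- Rule (c) lay within about −4 to +3 points of (a).
- Immature data (12-month accrual, cut-off at last entry): 6-month PFS was 0.2–1.9 points too low at 10–30% stopping. With the plan's 48-month accrual and a cut-off at last entry, the 4 / 8, 30% case was already too high (33.9 → 40.3).
- Partial capture (a similar model, 3-month median, about 26% stopping): with no capture, 12-month PFS read 16% against 8%. With routine 3-monthly scans retrieved for half of stoppers it read 12%, and for 80% of them 10%. The 6-month excess fell from 10 to 7 to 5 points.

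**Scale.** Ignoring censoring, the 90% half-width at a 6-month PFS of 34.6% is 1.645 × √(0.346 × 0.654 / n). That is 11.1 points at n = 50 (14.1) and 14.3 points at n = 30 (14.3). The 5.1-point excess in the 20% row is 36–46% of that half-width.

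**The case against.** The best defence is that the plan does not forbid looking for progression off treatment. PFS requires documented progression, not progression on a protocol scan. Section 5.7 already provides for chart review and contact with treating clinicians, 10.1.4.3 urges documentation after discontinuation, and the Section 10 opening is not confined to treatment. Some progressions will be found, so the simulated figures are upper bounds with respect to capture. PFS is also secondary and untested, and its sampling error is large. Finally, not everyone is followed to death: 5.6 allows withdrawal of consent, and some toxicity rules in Section 6 take patients off study, which fits 5.7 unclearly.

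All of this limits the size, but the gap remains. None of these texts sets a schedule off treatment. The 10.1.4.3 sentence sits in a note on symptomatic deterioration and does not make that deterioration an event. With 80% of routine scans retrieved, the excess shrank but persisted.

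Three stronger readings are tempting and not supported:
- **Late deaths also lengthen duration of response.** Under 10.1.5 and 14.1 that measure ends at documented recurrence or progression. Death is not an event in it, so this mechanism cannot act.
- **Responders who stop early lose confirmation, which erodes the primary endpoint and its power.** Section 10 asks for the confirmatory scan without tying it to treatment, and nothing in the documents says how many responders would be lost.
- **PFS becomes overall survival for everyone who stops.** That holds only for those who die with no progression documented.

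**Conclusion.** The point holds for PFS. As written, the plan schedules no tumour assessment after a stop without progression and counts any later death at its own date. The Kaplan-Meier estimates are therefore usually too high once follow-up is mature. The ranges of about 1–12 points at 6 months and 1–13 at 12 months rest on assumed stopping rates, progression and survival times, and on no capture off treatment. The true bias could be much smaller, is near zero if progression is slow, and may be slightly negative at an early cut-off. A reader should not infer that PFS is certain to be overstated, or that the trial's go/no-go decision is at risk. That decision rests on response counts among 21 and then 50 patients, which this does not touch. The issue is the credibility of a secondary descriptive result, and it is cheap to correct.

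**What to change.** 1. **Sections 10.1.6 and 14.1.** Add a sensitivity PFS analysis that censors at the last adequate disease assessment when death follows two or more missed 8-weekly assessments. Count missed assessments on the 8-weekly grid whether or not the patient is still on drug (a gap of more than 2 × 8 = 16 weeks, plus the visit window); otherwise nothing is formally missed after stopping. Add a second sensitivity analysis that counts symptomatic deterioration as an event.
2. **Section 5.7 and the Follow up/Survival Form.** For patients who stopped without RECIST progression, use the 3-monthly record review to collect routine scan results, the date of progression, and the start date of any new anticancer therapy.
3. **Reconcile the opening of Section 10 with 5.3, 5.7 and the calendar.** State whether 8-weekly and confirmatory assessments continue after treatment stops without progression. The two items above do not depend on adding scans.

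The cost is one amendment, a form change, some record retrieval in a minority of patients, and PFS figures that will probably look less favourable. Censoring after missed assessments has its own error (about −4 to +3 points here), so it belongs beside the main analysis as a sensitivity analysis.

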11. ADVERSE EVENT REPORTING REQUIREMENTS

11.1 Definitions

11.1.1 Adverse Event (AE)

An adverse event (AE) is any undesirable sign, symptom or medical condition or experience that develops or worsens in severity after starting the first dose of study treatment or any procedure specified in the protocol, even if the event is not considered to be related to the study.

Abnormal laboratory values or diagnostic test results constitute adverse events only if they induce clinical signs or symptoms or require treatment or further diagnostic tests.

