Any other grade 4 toxicity not listed here, including those involving the cardiac, endocrine, GI, metabolism, musculoskeletal, CNS, renal, respiratory, vascular, and cutaneous systems (CTCAE v4)	Hold Everolimus until recovery to grade \leq 1 or baseline value Reintroduce Everolimus at one dose level lower, if available. If resolution takes $>$ 28 days, the patient comes off the study.
Grade 3 or 4 clinical liver failure (asterixis or encephalopathy/coma)	Discontinue Everolimus
Recurrence of intolerable grade 2 mucositis or grade 3 event after dose reduction	Reduce dose to the next lower dose level, if available. The lowest possible dose level of Everolimus is 2.5 mg daily. Below this level, Everolimus must be discontinued.
Recurrence of grade 4 after dose reduction	Discontinue Everolimus
Any non-hematologic toxicity requiring Everolimus interruption for $>$ 28 days	Discontinue Everolimus, take patient off study
* Should HCV flare be confirmed, the guidelines for flare must take precedence	

Table 6-3 Dosing guidelines for Everolimus-related hematologic toxicities

Toxicity	Action
Grade 2 thrombocytopenia (platelets $<75, \geq 50 \times 10^9/L$)	No action
Grade 3 thrombocytopenia (platelets $<50, \geq 25 \times 10^9/L$)	Interrupt Everolimus until resolution to grade ≤ 1 If resolution occurs ≤ 7 days, reintroduce Everolimus at the dose level prior to interruption. If resolution occurs > 7 days, or event recurs within 28 days, reintroduce Everolimus at one dose level lower, if available. If resolution takes > 28 days, the patient comes off the study.
Grade 4 thrombocytopenia (platelets $< 25 \times 10^9/L$)	Interrupt Everolimus until recovery to grade ≤ 1 . Then reintroduce Everolimus at one dose level lower, if available. If resolution takes > 28 days, the patient comes off the study.
Grade 3 neutropenia or anemia (neutrophil $<1, \geq 0.5 \times 10^9/L$)	Interrupt Everolimus until resolution to grade ≤ 1 or baseline value If AE resolution occurs ≤ 7 days, reintroduce Everolimus at the same dose level. If AE resolution occurs > 7 days, or event recurs within 28 days, reintroduce Everolimus at one dose level lower, if available. If resolution takes > 28 days, the patient comes off the study.
Grade 4 neutropenia or anemia	Interrupt Everolimus until recovery to grade ≤ 1 or baseline value. Reintroduce Everolimus at one dose level lower, if available. * If resolution takes > 28 days, the patient comes off the study.

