11.2 Procedures for AE and SAE Recording and Reporting

Participating investigators will assess the occurrence of AEs and SAEs at all participant evaluation time points during the study.

All AEs and SAEs whether reported by the participant, discovered during questioning, directly observed, or detected by physical examination, laboratory test or other means, will be recorded in the participant's medical record and on the appropriate study-specific case report forms.

The descriptions and grading scales found in the revised NCI Common Terminology Criteria for Adverse Events (CTCAE) version 4.0 will be utilized for AE reporting. All appropriate treatment areas should have access to a copy of the CTCAE version 4.0. A copy of the CTCAE version 4.0 can be downloaded from the CTEP website at:

http://ctep.cancer.gov/protocolDevelopment/electronic_applications/ctc.htm.

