11.4 Reporting to the Study Sponsor

11.4.1 Serious Adverse Event Reporting

All serious adverse events that occur after the initial dose of study treatment, during treatment, or within 30 days of the last dose of treatment must be reported to the DF/HCC Overall Principal Investigator on the local institutional SAE form. This includes events meeting the criteria outlined in Section 11.1.2, as well as the following:

- Grade 2 (moderate) and Grade 3 (severe) Events – Only events that are unexpected and possibly, probably or definitely related/associated with the intervention.
- All Grade 4 (life-threatening or disabling) Events – Unless expected AND specifically listed in the protocol as not requiring reporting.
- All Grade 5 (fatal) Events – When the participant is enrolled and actively participating in the trial OR when the event occurs within 30 days of the last study intervention.

Note: If the participant is in long term follow up, report the death at the time of continuing review.

Participating investigators must report each serious adverse event to the DF/HCC Overall Principal Investigator within 1 business day of learning of the occurrence. In the event that the participating investigator does not become aware of the serious adverse event immediately (e.g., participant sought treatment elsewhere), the participating investigator is to report the event within 1 business day after learning of it and document the time of his or her first awareness of the adverse event. Report serious adverse events by telephone, email or facsimile to:

[name], PhD
[contact]

[contact]
 [contact]

Within the following 1-2 business days, the participating investigator must provide follow-up information on the serious adverse event. Follow-up information should describe whether the event has resolved or continues, if and how the event was treated, and whether the participant will continue or discontinue study participation.

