3.10 Safety Assessments and Toxicity Monitoring

The study teams at all participating institutions are responsible for protecting the safety, rights and well-being of study participants. Recording and reporting of adverse events that occur during the course of a study help ensure the continuing safety of study participants.

All participants receiving investigational agents and/or other protocol mandated treatment will be evaluated for safety. The safety parameters include all laboratory tests and hematological abnormalities, physical examination findings, and spontaneous reports of adverse events reported by participants. All toxicities encountered during the study will be evaluated according to the NCI criteria specified in the protocol. Life-threatening toxicities must be reported immediately to the DF/HCC Sponsor via the Coordinating Center.

Additional safety assessments and toxicity monitoring will be outlined in the protocol.

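### Section 11.1.1 has no CTCAE-grade or dose-change trigger for laboratory adverse events, so some grade 3-4 laboratory toxicity may be missing from the AE forms

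*Combined protocol and SAP*

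**What the plan says.** Section 11.1.1 first defines an adverse event broadly, then narrows it for laboratory findings: "Abnormal laboratory values or diagnostic test results constitute adverse events only if they induce clinical signs or symptoms or require treatment or further diagnostic tests". The rule is exclusive and has three triggers: symptoms or signs, treatment, and further tests.

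Other sections treat laboratory abnormalities as adverse events without that condition:

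- **Tables 6-2 and 6-3 (section 6.2)** interrupt everolimus on laboratory grade alone for AST/ALT, platelets, neutrophils and anemia. The grade 3 neutropenia or anemia row calls the finding an AE: "If AE resolution occurs ≤ 7 days, reintroduce Everolimus at the same dose level". The grade 3 AE row of Table 6-2 has to make an exception for raised glucose and lipids, which implies that laboratory findings are otherwise included.
- **Section 11.1.3.1** points to 6.1 as the list of expected adverse events. That list includes lymphocytopenia, neutropenia, anemia and AST/ALT increases.
- **Section 14.1** makes toxicity an estimated outcome: "We will also estimate toxicity via CTCAE version 4.0", with 90% exact binomial intervals. It does not name the data source.
- **Appendix C, section 3.10** says: "The safety parameters include all laboratory tests and hematological abnormalities".

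**The concern.** CTCAE grades most laboratory toxicity on the value itself. Section 11.1.1 decides whether that value becomes an adverse event on other grounds. A site that follows 11.1.1 literally can leave a grade 3 or 4 value off the AE form when the patient has no symptoms and nothing further is done. Another site may record the same value.

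Toxicity is a secondary objective (section 1.3). Any omission of this kind lowers the reported rate and never raises it, and it may vary between sites. If the toxicity table is built from AE forms, the forms alone cannot restore what was never entered.

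**Working it through.** The plan states no toxicity rate or safety threshold for this trial, so there is no figure to reproduce. The check follows three kinds of laboratory finding through the plan and then illustrates the possible size.

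**1. Which findings does the 11.1.1 rule capture?**

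- *Grade 3 neutropenia with a hold.* Table 6-3 holds drug until recovery, with cut-offs at 7 and 28 days. The study calendar (section 9) schedules blood tests every 4 weeks, extendable to every 8 weeks after cycle 2. A 7-day cut-off cannot be applied on a 28-day or 56-day schedule, so unscheduled counts are needed. On the ordinary reading the value requires further tests and is an AE. It drops out only if a site decides that repeating the same count is not a further diagnostic test. Section 11.1.1 does not settle this.
- *Raised cholesterol or triglycerides, grade 2 or higher.* Section 6.2.1.5 says these should be treated, so they meet the treatment trigger and are captured.
- *Asymptomatic grade 3 or 4 lymphocytopenia.* Section 6.1 lists it as hematologic, at up to 18% for grades 3/4. Table 6-3 has no row for it, and the catch-all rows of Table 6-2 belong to a table for non-hematologic toxicity. If the patient is well and nothing is done, no trigger is met. The differential count is part of scheduled hematology (section 9), so the value is measured but is not an AE.

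**2. Where else would an omitted value appear?** Section 12.1.2 lists eight forms for submission. They include a Treatment Form and an Adverse Event Report Form, but no laboratory form. Dose changes are recorded (section 5.1), which shows that a hold occurred but does not supply a graded toxicity. Where there was no hold, even that trace is absent. The AE form is the only evident route in that list for on-treatment laboratory toxicity.

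**3. Illustration of size.** Inputs: rate 18%, the upper figure in 6.1 for grade 3/4 lymphocytopenia; N = 60 (50 + 10 from 14.1) and N = 30 (section 14.3), since the plan gives both; missed share 0%, 25% or 50%, which is an assumption because the documents give none.

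Expected count = N × 0.18 × (1 − missed share), rounded to x. The 90% exact (Clopper-Pearson) limits are the 0.05 quantile of Beta(x, N − x + 1) and the 0.95 quantile of Beta(x + 1, N − x).

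| N | Missed (assumed) | Expected count | x/N | 90% exact interval |
|---|---|---|---|---|
| 60 | 0% | 10.8 | 11/60 = 18.3% | 10.6% to 28.5% |
| 60 | 25% | 8.1 | 8/60 = 13.3% | 6.8% to 22.8% |
| 60 | 50% | 5.4 | 5/60 = 8.3% | 3.3% to 16.7% |
| 30 | 0% | 5.4 | 5/30 = 16.7% | 6.8% to 31.9% |
| 30 | 25% | 4.05 | 4/30 = 13.3% | 4.7% to 28.0% |
| 30 | 50% | 2.7 | 3/30 = 10.0% | 2.8% to 23.9% |

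With nothing missed there is no bias. With 60 patients and half missed, the upper limit (16.7%) falls below the 18% that generated the data.

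**The case against.** The strongest reply is that the plan captures most of what matters. Holds need repeat tests, so held values normally qualify. Tables 6-2 and 6-3 and section 6.2.1 call laboratory findings AEs, which tells sites how to classify them. Section 11.2 covers events detected by "laboratory test or other means, will be recorded in the" medical record and on the case report forms. Appendix C 3.10 adds: "All toxicities encountered during the study will be evaluated according to the NCI criteria specified in the protocol". Monitoring visits review holds and reductions (Appendix C 5.1). Section 11.4.1 covers "All Grade 4 (life-threatening or disabling) Events" unless expected and listed as exempt. Section 14.1 does not confine the analysis to AE forms, so it is silent rather than contradictory.

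Much of this stands. A reader might infer that grade 3-4 toxicity leading to a hold goes unrecorded and that toxicity rates are therefore understated. The documents do not support that: held values are the best-covered case, the dose change is recorded elsewhere, and the missed share could be zero. Nor do they show that the safety committee would be misled. The AE item named in section 12.2 concerns unexpected events of grade 2 or higher, while the laboratory findings listed in 6.1 are generally expected.

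Three things remain. The lymphocytopenia case does not depend on how further tests are read. Section 11.2 governs the recording of AEs and SAEs, so it does not bring in a value that 11.1.1 has excluded. The grade 4 route has a similar limit: the table in 11.5 is set out by graded AEs, so whether an excluded value enters it is open. The conflicting wording in the tables may guide sites, but it does not amend an exclusive definition.

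**Conclusion.** The point holds in a limited form. Section 11.1.1 does not match the toxicity tables, the expected-event list or the CTCAE endpoint. Followed as written, it leaves out asymptomatic grade 3-4 values that need no treatment or further test, with lymphocytopenia the clearest example. For held values there is only an ambiguity about repeat counts, which sites may resolve differently.

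The consequence is possible under-recording on AE forms and possible understatement of laboratory toxicity rates, of unknown size. The illustrated fall from 18.3% to 13.3% or 8.3% at N = 60 rests on an upper-bound background rate and an assumed missed share. It also assumes that the toxicity table is built from AE forms, which the plan does not say. Response, the primary endpoint, is not affected, and section 14 makes no stopping rule depend on these rates. The matter is worth correcting because it concerns a stated secondary objective, the error can run only one way, and the correction is cheap.

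**What to change.** Add to 11.1.1: for recording purposes, a laboratory abnormality is also an adverse event if it is CTCAE v4.0 grade 3 or higher, or if it leads to interruption, reduction or discontinuation of everolimus. The first trigger closes the lymphocytopenia gap. The second makes the repeat-count question irrelevant for held values.

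Add to 14.1: laboratory toxicity is tabulated from these AE entries, or from graded laboratory values if those are captured in the database.

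The cost is one sentence in each section, more AE form entries, and somewhat higher reported toxicity rates. Grading directly from laboratory values would cost more than a sentence, because 12.1.2 lists no laboratory form. The sponsor should also state how grade 4 laboratory values recorded under the new rule are to be handled under 11.4.1 and 11.5, since they would then clearly be graded AEs.
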